16.3 STUDY ENDPOINTS

During interim analysis (at 6 months of treatment) and final analysis at the end of treatment, the following endpoints will be evaluated:

16.3.1 Primary Efficacy Endpoint:

- Compare the mean relative change in ALT & AST levels between the experimental arms and the control arm.
- Compare proportions of patients with normal ALT & AST at end of treatment between the experimental arms and the control arm. The cut-off values of ALT were 0-43 IU/L and of AST were 0-40 IU/L⁷.

16.3.2 Secondary Efficacy Endpoints:

- Comparing the mean change in Fib-4 score between the experimental arms and the control arm.
- Comparing the frequency and percentage of patients experiencing hepatic complications

⁶ Gpower 3.1

⁷ Uslusoy H, Nak S, Gülten M, Bıyıklı Z. Non-alcoholic steatohepatitis with normal aminotransferase values. World Journal of Gastroenterology. 2009;15(15):1863.

between the experimental arms and control arm.

16.3.3 Exploratory Endpoint:

- Compare the mean relative change in lipid profile levels between the experimental arms and the control arm.

16.4 STATISTICAL ANALYSES

The statistical analysis of this study will consist of reporting of individual data listings, providing descriptive statistics for parameters of interest, and statistical testing of the primary and secondary variables.

The final statistical analyses will be performed when the patients on Heptex and placebo complete 9 months of treatment.

Detailed analysis methods will be provided in the statistical analysis plan.

16.4.1 Descriptive analysis:

- Percent (%) distribution for all categorical variables and mean with (SD) and median (Minimum: Maximum) for continuous variables according their distribution.

16.4.2 Primary analysis:

- The main objectives of this phase II study is to explore the anti-oxidant activity of Heptex as assessed by improvement in serum aspartate aminotransferase (AST) and alanine aminotransferase (ALT) levels by measuring:
- The mean relative change in ALT & AST levels between the experimental arms and the control arm from baseline till end of treatment using T-test (Mann-Whitney test in case of non-parametric data). This analysis will be a comparative analysis and will be done on eligible population of patients without protocol violation and who have at least one treatment dose and an evaluable primary endpoint (AST and ALT).
- Number of patients with normal ALT & AST at end of treatment between the experimental arms and the control arm. The cut-off values of ALT were 0-43 IU/L and of AST were 0-40 IU/L⁸ using chi square (Fischer test for non-parametric data). This analysis will be comparative analysis and will be conducted on the eligible population of patients without protocol deviation, who have at least one treatment dose and an evaluable primary endpoint (ALT and AST).

All tests will be performed on the 5% level of significance.

⁸ Uslusoy H, Nak S, Gülten M, Bıyıklı Z. Non-alcoholic steatohepatitis with normal aminotransferase values. World Journal of Gastroenterology. 2009;15(15):1863.

Procedure for accounting for missing, unused, and spurious data will be explained in the statistical analysis plan.

Any deviation(s) from the original statistical plan will be described in the final report).

16.4.3 Secondary analysis:

- The mean change in Fib-4 score between the experimental arms and the control arm from baseline till end of treatment using T-test (Mann-Whitney test in case of non-parametric data). This analysis will be a comparative analysis and will be done on eligible population of patients without protocol violation and who have at least one treatment dose and an evaluable primary endpoint (AST and ALT).
- Number of patients experiencing hepatic complications between the experimental arms and control arm at the end of the treatment using chi-square (Fischer for non-parametric data). This analysis will be a comparative analysis and will be done on eligible population of patients without protocol violation and who have at least one treatment dose and an evaluable primary endpoint (AST and ALT).

16.4.4 Exploratory analysis:

- The mean relative change in lipid profile levels between the experimental arms and the control arm from baseline till end of treatment using T-test (Mann-Whitney test in case of non-parametric data). This analysis will be a comparative analysis and will be done on eligible population of patients without protocol violation and who have at least one treatment dose and an evaluable primary endpoint (AST and ALT).

16.4.5 Interim analysis:

- Interim analysis will be performed when all patients complete 6 months of treatment. If a statistically significant difference is observed between placebo and active arm(s), the study will be terminated for the benefit of patients who were randomly assigned to placebo arm and to rapidly disseminate evidence supporting a treatment benefit to the broader community⁹.

⁹Zannad F, et al. Development of Therapeutics for Heart Failure. When to Stop a Clinical Trial Early for Benefit: Lessons Learned and Future Approaches. *Circulation: Heart Failure*. 2012; 5: 294-302. doi: 10.1161/CIRCHEARTFAILURE.111.965707

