
Statistical methodologies
	
Statistical Power and Sample Size Justification³
 
Reference to Sanyal AJ, et al. there was a decrease in Alanine aminotransferase level among placebo arm of -20 (U/liter) among the placebo arm while for the active arm, a double of this improvement will be of clinical value. Accordingly, with an alpha error of 5% using one-sided 95% CI of Mann–Whitney U test, a sample power of 80% and an effect size between placebo and lowest active dose of 0.63, a sample of 43 patients for each arm will be required plus an expected drop-out rate of 10% during 9 months’ study duration. Thus, a sample of 47 patients per each treatment arm will be appropriate and the total same of the 3 arms will be 141 patients.
 
Randomization method:
 
The arms randomization will be performed using Interactive web response system (IWRS).
 
Statistical methodologies:
 
The statistical analysis of this study will consist of reporting the individual data listings, providing descriptive statistics for parameters of interest, and statistical testing of the primary and secondary variables.
 
The final statistical analyses will be performed when the patients on Heptex and placebo complete 9 months of treatment.
 
Detailed analysis methods will be provided in the statistical analysis plan.

3 Gpower 3.1

Descriptive analysis:

Percent (%) distribution for all categorical variables and mean with (SD) and median (Minimum: Maximum) for continuous variables according their distribution.

Primary analysis:

The main objectives of this phase II study is to explore the anti-oxidant activity of Heptex as assessed by improvement in serum aspartate aminotransferase (AST) and alanine aminotransferase (ALT) levels by measuring:

- The mean relative change in ALT & AST levels between the experimental arms and the control arm from baseline till end of treatment using T-test (Mann-Whitney test in case of non-parametric data). This analysis will be a comparative analysis and will be done on eligible population of patients without protocol violation and who have at least one treatment dose and an evaluable primary endpoint (AST and ALT).

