2 ASSESMENT SCHEDULE

Data to be collected	Study Schedule*					
	V1 screening	V2 Week 0	V3 Week 8	V4 Week 12	V5 Week 24	V6 Week 36
Informed consent	X					
Inclusion/ exclusion criteria	X					
Demographics	X					
Medical/ Surgical history	X					
Concomitant medications	X	X	X	X	X	X
Physical examination	X	X	X	X	X	X
Vital signs	X	X	X	X	X	X
Fibroscan liver stiffness measurement	X				X	X
Fib-4	X		X	X	X	X
Abdominal Ultrasound	X					
Controlled Attenuation Parameter (CAP)	X		X	X	X	X
Serum pregnancy test for females	X		X	X	X	X
PCR	X					
Alpha fetoprotein	X					
HCV RNA	X					
HAV IgM	X					
HBsAg	X					
CBC	X		X	X	X	X
Sodium	X				X	X
Potassium	X				X	X
Serum Fibrinogen	X		X	X	X	X
Liver Profile tests - Albumin, bilirubin, - PT, PTT, INR, - ALT and AST	X		X	X	X	X
Kidney function tests	X				X	X
Lipid Profile	X				X	X
HbA1c	X				X	X
Study drug dispensed		X	X	X	X	
Drug Accountability			X	X	X	X
Adverse Events Serious Adverse Events Hepatic complications		X	X	X	X	X
Study Completion Form						X

* Washout periods at week 13 and week 25.

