8.4 DATA TO BE COLLECTED AT DIFFERENT STUDY INTERVALS

Screening visit:

During screening visit, data on informed consent process, inclusion and exclusion criteria, demographics, medical and surgical history, concomitant medications, physical examination, vital signs, FibroScan liver stiffness measurement (KPa), abdominal ultrasound, controlled attenuation parameter (CAP), lab tests (serum pregnancy test for females, PCR; HCV RNA, HAV IgM antibody test, HBsAg test, alpha fetoprotein, CBC, sodium, potassium, serum fibrinogen, albumin, bilirubin, prothrombin time, PTT, INR, ALT, AST, kidney function tests, lipid profile, and HbA1c) will be collected. Then Fib-4 score will be calculated.

Baseline (week 0):

At baseline visit, data on concomitant medications, physical examination and vital signs will be collected. Then occurrence of adverse events and serious adverse events

including hepatic complications will be collected. Data on the dispensed drug will be recorded.

Week 8 and week 12:

At week 8 and week 12, data on concomitant medications, physical examination, vital signs, controlled attenuation parameter (CAP), lab tests (serum pregnancy test for females, CBC, serum fibrinogen, albumin, bilirubin, prothrombin time, PTT, INR, ALT and AST) will be collected. Then Fib-4 score will be calculated and occurrence of adverse events and serious adverse events including hepatic complications will be collected. The drug accountability for the dispensed drug will be recorded.

Week 24:

At week 24, data on concomitant medications, physical examination, vital signs, FibroScan liver stiffness measurement (KPa), controlled attenuation parameter (CAP), lab tests (serum pregnancy test for females, CBC, sodium, potassium, serum fibrinogen, albumin, bilirubin, prothrombin time, PTT, INR, ALT, AST, kidney function tests, lipid profile and HbA1c) will be collected. Then Fib-4 score will be calculated and occurrence of adverse events and serious adverse events including hepatic complications will be collected. The drug accountability for the dispensed drug will be recorded.

Week 36:

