9.2 INCLUSION CRITERIA

- 1) Male or female aged between 18 and 65 years.
- 2) Both male and female patients who have childbearing potential must agree to practice an acceptable method of birth control during the study and for at least 6 months after the cessation of treatment; such contraceptive methods must include at least one barrier method.
- 3) Controlled Attenuated Parameter (CAP)-confirmed hepatic steatosis.
- 4) Patients with elevated Liver enzymes (ALT and/or AST) ^[34].
- 5) Liver fibrosis stage F1-F2 as diagnosed by the FibroScan liver stiffness measurement of 5-10 kPa.
- 6) liver condition according the following criteria;
 - Serum albumin > 3 g/dl
 - INR < 2
 - No ascites on ultrasound
 - No documented or suspected hepatic encephalopathy
- 7) Willing to stop any other liver support and hepatoprotective medications throughout study duration.
- 8) Able and willing to provide written informed consent.
- 9) Able and willing to complete all study visits and procedures, including compliance with the requirements and restrictions listed in the consent form.

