16 STATISTICAL CONSIDERATIONS

16.1 SAMPLE SIZE CALCULATION⁶

Reference to Sanyal AJ, et al. There was a decrease in Alanine aminotransferase level among placebo arm of -20 (U/liter) among the placebo arm while for the active arm, a double of this improvement will be of clinical value. Accordingly, with an alpha error of 5% using one-sided 95% CI of Mann–Whitney U test, a sample power of 80% and an effect size between placebo and lowest active dose of 0.63, a sample of 43 patients for each arm will be required plus an expected drop-out rate of 10% during 9 months' study duration. Thus, a sample of 47 patients per each treatment arm will be appropriate and the total same of the 3 arms will be 141 patients.

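### The primary ALT/AST comparison is fixed as an unadjusted test of relative change; adding the screening value as a covariate is a cheap, optional precision gain

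*Protocol*

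**What the plan says.** Section 16.3.1 gives the first primary endpoint as "Compare the mean relative change in ALT & AST levels between the experimental arms and the control arm". Section 16.4.2 names the test: "mean relative change in ALT & AST levels between the experimental arms and the control arm from baseline till end of treatment using T-test", with Mann-Whitney for non-parametric data. The synopsis has the same: "from baseline till end of treatment using T-test (Mann-Whitney test in case of non-parametric data". The analysis text mentions no covariate, ANCOVA or regression model. Section 16.4 leaves detailed methods to the SAP, but the protocol itself names the test.

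In the assessment schedule (section 2), the row "Liver Profile tests - Albumin, bilirubin, - PT, PTT, INR, - ALT and AST" is marked at screening and at Weeks 8, 12, 24 and 36, with no mark at Week 0. Section 8.4 agrees: "At baseline visit, data on concomitant medications, physical examination and vital signs will be collected", and it lists no laboratory test for that visit. The screening sample is therefore the only scheduled pre-treatment ALT/AST. Inclusion criterion 4 requires ALT and/or AST to be raised, so patients are selected on the marker that is later analysed.

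On size, section 16.1 says "a sample of 43 patients for each arm will be required", "with an alpha error of 5% using one-sided 95% CI", with an effect size of 0.63 and 80% power. Ten percent dropout brings this to 47 per arm.

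**The concern.** Dividing by the screening value is not the same as adjusting for it. Where screening and later values are imperfectly correlated, patients with high screening values tend to show the larger percentage falls, whatever their arm. An unadjusted t-test or rank test counts that predictable part as noise. A covariate that is already collected would remove some of it.

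Only precision is at stake. Randomisation keeps the planned comparison valid, and the rank fallback deals with skewness. With 47 × 0.9 ≈ 42 evaluable patients per arm there is little spare power, so a costless gain deserves a look.

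**Working it through.** **1. The plan's own figure.** Take the Mann-Whitney as a t-test with n scaled by its efficiency 3/π, effect size d = 0.63 and 5% two-sided. At n = 43 the effective size is 43 × 0.955 = 41.1 and the noncentrality is 0.63 × √(41.1/2) = 2.86, which gives 80.5% power. At n = 42 power is 79.6%. So 43 reproduces as a two-sided calculation; the one-sided wording would give 34. Two-sided 5% is therefore the main case below.

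**2. What the planned test leaves unused.** Let r be the correlation of log screening with log end-of-treatment value, and k the ratio of the end-of-treatment log SD to the screening log SD. The slope of log change on log screening value is r·k − 1.

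- With k = 1 the slope is −0.5, −0.3, −0.2 and −0.1 at r = 0.5, 0.7, 0.8 and 0.9. Without entry restriction, the share of log-change variance explained is (1 − r)/2, that is 25%, 15%, 10% and 5%.
- On the planned percent-change scale, with entry restricted to ALT above 43, the simulated correlation with log screening ALT is −0.24 to −0.42 at r = 0.5 to 0.7. That explains 0.24² = 6% to 0.42² = 18% of the variance.
- With k = 1.25 and r = 0.8, the slope is 0.8 × 1.25 − 1 = 0, and nothing is left to adjust for.

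**3. Power, by simulation.** Assumptions that the protocol does not supply: bivariate lognormal values, log SD 0.42 at both times (k = 1), screening ALT above 43 (the upper limit of normal in 16.3.1), median ALT 45, 60 or 80 before that cut, and 43 per arm. The effect is set so that the planned t-test has about 80% power at each r. Gains are in percentage points across the three medians.

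| r | Active/placebo ratio | Covariate added to percent change | Covariate and log scale |
|---|---|---|---|
| 0.5 | about 0.77–0.79 | +2.8 to 6.7 | +5.6 to 9.7 |
| 0.7 | about 0.82 | +2.0 to 4.1 | +4.0 to 5.9 |
| 0.8 | about 0.85 | +1.1 to 3.4 | +2.3 to 4.7 |
| 0.9 | about 0.89 | +0.2 to 2.4 | +0.9 to 3.1 |

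Example, median 60 and r = 0.5: t-test 80.3%, Mann-Whitney 80.6%, percent-change ANCOVA 85.3%, log-scale ANCOVA 88.0%.

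**4. Sensitivity, true reduction fixed at 20%.**

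- *Unequal spread (median 60).* At r = 0.8, k = 1.25, adding the covariate takes power from 88.8% to 88.5%. At r = 0.7, k = 1.2, from 77.3% to 77.4%. The gain has gone.
- *No cut at 43.* Because entry is on ALT and/or AST, some patients may enter with normal ALT. The covariate alone then adds about 10 points at r = 0.5 (t-test 64.8%, Mann-Whitney 66.0%, adjusted 75.6%) and about 4 at r = 0.7 (86.3%, 86.5%, 90.8%).
- *One-sided 5%.* The covariate alone adds 2.8 to 6.2 points at r = 0.5 and 0.8 to 2.0 at r = 0.7.
- *Type I error* (no effect, median 60, r = 0.5 and 0.7) is 4.9% to 5.1% for every method.

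**The case against.** - **Nothing in the document is in error here.** The test is valid, already uses the screening value as divisor, and 43 per arm reproduces for it. This stands, and it makes the point an improvement, not a correction.
- **Covariates are often left to an SAP.** An SAP may well contain a supportive adjusted analysis; that cannot be excluded. But the protocol fixes the primary test itself, so replacing it needs a protocol change.
- **The effect in section 16.1 is not a 20% reduction.** A fall of 20 U/L on placebo and 40 on active gives an active/placebo ratio of (60 − 40)/(60 − 20) = 0.50 from a start of 60, and 40/60 = 0.67 from 80; 0.80 needs a start of 120 (80/100). At 0.50 and 0.67 with log SD 0.42, the planned test has 99–100% power at r = 0.5 and 0.7, leaving at most about 0.5 point to gain. From a start of 100 (60/80 = 0.75), at r = 0.5, adjustment still takes power from 86.7% to 92.7%. This stands, which is why the size is read from the runs that start at 80% power. Section 16.1 does imply an SD of 20/0.63 = 31.7 U/L for absolute change, but without a starting level that does not fix the spread of relative change.
- **Adjustment need not help.** A reader might infer that a covariate must raise power. The documents do not support that: they give neither the correlation nor the ratio of spreads, and step 4 shows plausible values with no gain. The log scale still gains 1.3 to 2.6 points in similar unequal-spread runs, but largely because the outcome scale changes.
- **The log scale alters the endpoint.** It replaces mean relative change with a ratio of geometric means. This stands, so that version is optional.

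**Conclusion.** The point holds as a low-priority improvement. The protocol fixes an unadjusted primary comparison and leaves the screening value unused beyond its role as divisor. Given a correlation of 0.5 to 0.9, log SD 0.42, equal log SDs at both times, entry at ALT above 43, and about 80% starting power, the covariate alone is worth about 0 to 7 points of power. The gain is largest near r = 0.5 and essentially nil if end-of-treatment values are clearly more spread out than screening values. With the log scale it is about 1 to 10 points. The fair summary of direction is a gain or no material loss.

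A reader might also infer that the planned result would be biased or the trial too small. Neither follows: the loss is precision only, and the sample was sized for the planned test. The second primary endpoint, normalisation of ALT and AST, is not affected.

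**What to change.** In section 16.4.2 and the synopsis, make the primary comparison of relative change an ANCOVA for each enzyme, with treatment and the log screening value of that enzyme as terms. State that baseline ALT/AST means the screening value. Use the same model at the interim, and keep the planned t-test or Mann-Whitney as a sensitivity analysis.

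Optionally, analyse log end-of-treatment value on treatment and log screening value, reported as a ratio of geometric means against placebo. Section 16.3.1 must then be aligned, because the summary measure changes.

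The cost is one degree of freedom per model and a protocol amendment submitted to the ethics committee under section 17.4, which could be combined with other amendments. No patient, visit or assay is added, and 43 evaluable per arm can stand.

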- Number of patients with normal ALT & AST at end of treatment between the experimental arms and the control arm. The cut-off values of ALT were 0-43 IU/L and of AST were 0-40 IU/L⁴ using chi square (Fischer test for non-parametric data). This analysis will be comparative analysis and will be conducted on the eligible population of patients without protocol deviation, who have at least one treatment dose and an evaluable primary endpoint (ALT and AST).

Secondary Analysis:

- The mean change in Fib-4 score between the experimental arms and the control arm from baseline till end of treatment using T-test (Mann-Whitney test in case of non-parametric data). This analysis will be a

comparative analysis and will be done on eligible population of patients without protocol violation and who have at least one treatment dose and an evaluable primary endpoint (AST and ALT).

- Number of patients experiencing hepatic complications between the experimental arms and control arm at the end of the treatment using chi-square (Fischer for non-parametric data). This analysis will be a comparative analysis and will be done on eligible population of patients without protocol violation and who have at least one treatment dose and an evaluable primary endpoint (AST and ALT).

Exploratory Analysis:

- The mean relative change in lipid profile levels between the experimental arms and the control arm from baseline till end of treatment using T-test (Mann-Whitney test in case of non-parametric data). This analysis will be a comparative analysis and will be done on eligible population of patients without protocol violation and who have at least one treatment dose and an evaluable primary endpoint (AST and ALT).

All tests will be performed on the 5% level of significance.

Procedure for accounting for missing, unused, and spurious data will be explained in the statistical analysis plan.

Any deviation(s) from the original statistical plan will be described in the final report).

Interim analysis:

Interim analysis will be performed when all patients complete 6 months of treatment. If a statistically significant difference is observed between placebo and active arm(s), the study will be terminated for the benefit of patients who

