16.2 ANALYSIS POPULATIONS

The obtained clinical data will be analyzed on an intention-to-treat basis. Primary analysis will be done by intention-to-treat including all eligible enrolled patients with at least one treatment dose and post first dose assessment (ALT & AST) attending any post treatment visit and efficacy variables will be analyzed using the last-observation-carried-forward convention (LOCF).

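### Section 16.2 sets a modified intention-to-treat primary analysis, while Section 16.4.2 and the synopsis exclude protocol violators or deviators from the same tests, and nothing says which set prevails

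*Protocol*

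**What the plan says.** Section 16.2 states the general rule, "The obtained clinical data will be analyzed on an intention-to-treat basis", and then the specific one: "Primary analysis will be done by intention-to-treat including all eligible enrolled patients with at least one treatment dose and post first dose assessment". The assessment meant is ALT and AST at any post-treatment visit, and efficacy variables are handled by LOCF. The section contains no exclusion for violations or deviations.

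Section 16.4.2, headed as the primary analysis, describes two tests. The comparison of mean relative change in ALT and AST "will be done on eligible population of patients without protocol violation and who have at least one treatment dose and an evaluable primary endpoint". The comparison of patients with normal ALT and AST "will be conducted on the eligible population of patients without protocol deviation, who have at least one treatment dose and an evaluable primary endpoint".

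The synopsis repeats both restrictions. Relative change "will be done on eligible population of patients without protocol violation and who have at least one treatment dose"; for normalisation it says "This analysis will be comparative analysis and will be conducted on the eligible population of patients without protocol deviation". It mentions neither intention-to-treat nor LOCF.

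The secondary tests (Fib-4 and hepatic complications, 16.4.3) and the exploratory test (lipids, 16.4.4) exclude violators too, both in the body and in the synopsis.

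Sections 16.4.5 and 19 end the study if the interim analysis is statistically significant (in favour of active treatment, in Section 19). Section 16.3 says that the interim evaluates the same endpoints. Neither 16.4.5 nor 19 names an analysis set.

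**The concern.** The protocol fixes the primary analysis set twice, in incompatible ways, and does not call either set supportive. An analyst could follow either section and claim to have followed the protocol, and any choice made in the SAP would contradict one of them.

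Three things are at stake. First, both primary tests are affected, and a violation-free set removes patients for what happens after randomisation, so the arms compared may no longer be the arms randomised. Second, an interim result that can end the trial inherits the same open choice. Third, the two primary tests use different words, violation for one and deviation for the other. With neither defined, they could be run on different patients.

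A related but separate weakness concerns hepatic complications. That test is limited to patients without a violation who have evaluable AST and ALT, so it can lose patients who had the outcome being counted.

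**Working it through.** **1. The sets side by side**

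| Requirement | 16.2 | 16.4.2, relative change | 16.4.2, normalisation |
|---|---|---|---|
| Eligible | yes | yes | yes |
| At least one dose | yes | yes | yes |
| ALT/AST after dosing | yes, any visit | evaluable endpoint | evaluable endpoint |
| Excluded for conduct | none | protocol violation | protocol deviation |
| Missing values | LOCF | left to the SAP | left to the SAP |

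The synopsis matches the two right-hand columns on the exclusion. The only firm difference in membership is the exclusion row.

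**2. How often each rule appears**

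- Sections 16.4.2 to 16.4.4: 5 analyses (2 primary, 2 secondary, 1 exploratory); 4 exclude violations and 1 excludes deviations.
- Synopsis: the same 5 analyses, again 4 and 1.
- Total: 10 of 10 statements exclude (8 violation, 2 deviation). As the synopsis copies the body, this is five rules stated twice.
- Intention-to-treat appears only in 16.2.

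**3. Do the sets differ in practice?**

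Take a patient who is randomised, dosed, has ALT/AST measured at week 8 and then violates the protocol. Under 16.2 the patient stays, with the last value carried forward. Under 16.4.2 the patient is removed. The protocol itself names routes to such cases: Section 18 lists significant deviation and significant non-compliance as withdrawal grounds, and Section 11 withdraws a patient who needs other liver-support, hepatoprotective or prohibited medication. The last of these may be related to outcome.

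**4. Is the choice left to the SAP?**

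Section 16.4 defers detailed methods, and 16.4.2 defers the handling of missing, unused and spurious data. Neither defers the choice of population, which the protocol states itself.

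**5. Size**

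The bias cannot be computed, because no violation rate and no relation of violations to outcome is given. What can be illustrated is the cost in power, with the exclusion rate as an assumption.

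Inputs from Section 16.1: effect size d = 0.63, power 80%, 43 per arm, 47 after allowing for 10% drop-out. Method: t-test power at an effective size n × 3/π per arm (Mann-Whitney efficiency for normal data), noncentrality d × √(effective n / 2), degrees of freedom 2 × effective n − 2.

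The plan's own figure first: two-sided 5% gives exactly 43 per arm, while the one-sided 5% written in 16.1 gives 34. That mismatch is a separate matter, so both conventions are shown. For drop-out, 43 × 1.10 = 47.3, which agrees with 47. This allowance is for drop-out only and does not cover removal of violators.

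| Assumed share of the 43 excluded | n per arm | Power, two-sided 5% | Power, one-sided 5% |
|---|---|---|---|
| 0% | 43.0 | 80.5% | 88.2% |
| 5% | 40.9 | 78.4% | 86.7% |
| 10% | 38.7 | 76.2% | 85.0% |
| 20% | 34.4 | 71.0% | 81.1% |
| 30% | 30.1 | 65.1% | 76.2% |

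These figures hold d at 0.63 in every row. They show loss of numbers, not bias, and the point does not depend on them.

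**6. Hepatic complications**

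The first scheduled ALT/AST after dosing is at week 8 (Section 2). A dosed patient who has a complication and leaves before that has no post-dose ALT/AST, and so is in neither set. A patient who has a complication and also violates the protocol is in the 16.2 set but is dropped by 16.4.3. In both cases the event is still recorded as an adverse event (Sections 15.1 and 15.17), but the patient is missing from the test.

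**The case against.** Four objections deserve an answer.

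*The trial is exploratory and a SAP may settle the set before unblinding.* The objectives are indeed worded as exploration, and this softens the consequence. It does not remove a contradiction inside the protocol, which also attaches a stopping rule to a significance test on these endpoints.

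*The 16.2 set is not pure intention-to-treat.* This stands. It drops randomised patients with no dose or no post-dose ALT/AST, so making it primary leaves some post-randomisation exclusion in place. It should be called modified intention-to-treat. Nor does adopting it endorse LOCF: 16.2 fixes LOCF while 16.4.2 leaves missing-data handling to the SAP, and that wording needs aligning too.

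*The loss of early leavers from the hepatic-complications test is not part of the contradiction.* This also stands. Both sets require a post-dose ALT/AST, so both lose such a patient; only the violator is treated differently. The protocol does not say that a complication is itself a violation, so the overlap is possible but not shown.

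*A reader might infer more from the visit schedule.* Hepatic complications are listed at five visits and post-dose ALT/AST at four, which could suggest a treatment visit where complications are collected without enzymes. The documents do not support that. The extra visit is week 0, when patients are randomised and first given study drug. After that, both fall at weeks 8, 12, 24 and 36. Complications between visits reach the record through continuous adverse-event recording.

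**Conclusion.** The contradiction is real and should be resolved before any unblinded analysis. One section keeps patients who violate the protocol in the primary analysis; the section that describes the primary tests, and the synopsis, remove them; and no rule of precedence exists. Both primary tests are affected, and through Section 16.3 so is the interim analysis that can stop the trial.

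The direction of any bias is unknown and its size cannot be computed from the protocol. If 10 to 20% of the 43 per arm were excluded as violators, an assumed range, power would be about 76 to 71% at two-sided 5%, or 85 to 81% at the one-sided 5% as written.

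A reader might also infer that the sponsor intends to choose the set after seeing results, or that hepatic complications would go unreported. The text supports neither. It shows an unranked choice, and complications remain in the adverse-event record even where the patient is absent from the test.

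**What to change.** 1. Name the 16.2 set as the primary set, call it modified intention-to-treat, and use the same wording in 16.2, 16.4.2 to 16.4.4 and the synopsis.
2. State in 16.4.5 that the interim analysis uses the same set.
3. Keep the violation-free set as a sensitivity analysis, under one defined term in place of violation and deviation, with membership fixed before unblinding.
4. As a separate correction and the one exception to item 1, compare hepatic complications in all patients who took at least one dose, whether or not they violated the protocol or have an evaluable ALT/AST.

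The cost is wording in the protocol and SAP, with no new data, since LOCF is already set in 16.2 and complications are already collected. The estimate may differ from that in the violation-free set, in either direction. For the complications comparison, early leavers contribute only the events recorded for them, so incomplete follow-up remains a limitation to report.
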